8.3 ADVERSE EVENTS AND SERIOUS ADVERSE EVENTS

8.3.1 DEFINITION OF ADVERSE EVENTS (AE)

Adverse event means any untoward medical occurrence associated with the use of an intervention in humans, whether or not considered intervention-related (21 CFR 312.32 (a)).

8.3.2 DEFINITION OF SERIOUS ADVERSE EVENTS (SAE)

An adverse event (AE) or suspected adverse reaction is considered "serious" if, in the view of either the investigator or sponsor, it results in any of the following outcomes: death, a life-threatening adverse event, inpatient hospitalization or prolongation of existing hospitalization, a persistent or significant incapacity or substantial disruption of the ability to conduct normal life functions, or a congenital anomaly/birth defect. Important medical events that may not result in death, be life-threatening, or require hospitalization may be considered serious when, based upon appropriate medical judgment, they may jeopardize the participant and may require medical or surgical intervention to prevent one of the outcomes listed in this definition. Examples of such medical events include seizures that do not result in inpatient hospitalization, or the development of drug dependency or drug abuse.

8.3.3 CLASSIFICATION OF AN ADVERSE EVENT

8.3.3.1 SEVERITY OF EVENT

For adverse events (AEs), not included in the protocol defined grading system, the following guidelines will be used to describe severity.

- **Mild** – Events require minimal or no treatment and do not interfere with the participant's daily activities.
- **Moderate** – Events result in a low level of inconvenience or concern with the therapeutic measures. Moderate events may cause some interference with functioning.
- **Severe** – Events interrupt a participant's usual daily activity and may require systemic drug therapy or other treatment. Severe events are usually potentially life-threatening or incapacitating. Of note, the term "severe" does not necessarily equate to "serious".

8.3.3.2 RELATIONSHIP TO STUDY INTERVENTION

All adverse events (AEs) must have their relationship to study intervention assessed by the clinician who examines and evaluates the participant based on temporal relationship and his/her clinical judgment. The degree of certainty about causality will be graded using the categories below. In a clinical trial, the study product must always be suspect.

- **Definitely Related** – There is clear evidence to suggest a causal relationship, and other possible contributing factors can be ruled out. The clinical event, including an abnormal laboratory test result, occurs in a plausible time relationship to study intervention administration and cannot be explained by concurrent disease or other drugs or chemicals. The response to withdrawal of the study intervention (dechallenge) should be clinically plausible. The event must be

pharmacologically or phenomenologically definitive, with use of a satisfactory rechallenge procedure if necessary.

- **Probably Related** – There is evidence to suggest a causal relationship, and the influence of other factors is unlikely. The clinical event, including an abnormal laboratory test result, occurs within a reasonable time after administration of the study intervention, is unlikely to be attributed to concurrent disease or other drugs or chemicals, and follows a clinically reasonable response on withdrawal (dechallenge). Rechallenge information is not required to fulfill this definition.
- **Potentially Related** – There is some evidence to suggest a causal relationship (e.g., the event occurred within a reasonable time after administration of the trial medication). However, other factors may have contributed to the event (e.g., the participant's clinical condition, other concomitant events). Although an AE may rate only as "possibly related" soon after discovery, it can be flagged as requiring more information and later be upgraded to "probably related" or "definitely related", as appropriate.
- **Unlikely to be related** – A clinical event, including an abnormal laboratory test result, whose temporal relationship to study intervention administration makes a causal relationship improbable (e.g., the event did not occur within a reasonable time after administration of the study intervention) and in which other drugs or chemicals or underlying disease provides plausible explanations (e.g., the participant's clinical condition, other concomitant treatments).
- **Not Related** – The AE is completely independent of study intervention administration, and/or evidence exists that the event is definitely related to another etiology. There must be an alternative, definitive etiology documented by the clinician.

8.3.3.3 EXPECTEDNESS

The PI as well as the research coordinator assisting the PI will be responsible for determining whether an adverse event (AE) is expected or unexpected. An AE will be considered unexpected if the nature, severity, or frequency of the event is not consistent with the risk information previously described for the study intervention.

8.3.4 TIME PERIOD AND FREQUENCY FOR EVENT ASSESSMENT AND FOLLOW-UP

The occurrence of an adverse event (AE) or serious adverse event (SAE) may come to the attention of study personnel during study visits and interviews of a study participant presenting for medical care, or upon review by a study monitor.

All AEs including local and systemic reactions not meeting the criteria for SAEs will be captured on the appropriate case report form (CRF). Information to be collected includes event description, time of onset, clinician's assessment of severity, relationship to study product (assessed only by those with the training and authority to make a diagnosis), and time of resolution/stabilization of the event. All AEs occurring while on study must be documented appropriately regardless of relationship. All AEs will be followed to adequate resolution.

Any medical condition that is present at the time that the participant is screened will be considered as baseline and not reported as an AE. However, if the study participant's condition deteriorates at any time during the study, it will be recorded as an AE. Thus, in the case of a worsening of symptoms leading to a worsening of the patient's condition, antipsychotic medication can be given on the ward if the responsible MD thinks that this is necessary for the patient's health. Patients' well-being is the main priority even if this means the termination from the study because of the antipsychotic.

Changes in the severity of an AE will be documented to allow an assessment of the duration of the event at each level of severity to be performed. AEs characterized as intermittent require documentation of onset and duration of each episode.

The PI as well as the research coordinator assisting the PI will record all reportable events with start dates occurring any time after informed consent is obtained until 7 (for non-serious AEs) or 30 days (for SAEs) after the last day of study participation. At each study visit, the investigator will inquire about the occurrence of AE/SAEs since the last visit. Events will be followed for outcome information until resolution or stabilization.

8.3.5 ADVERSE EVENT REPORTING

Side-effects will be monitored by the study physician and self-reports. Treatment side effects will be measured using the Treatment Emergent Side Effects Scale (TESS). Reported adverse events will be evaluated and treated according to standard treatments procedures. In the case of a serious or intolerable adverse event subjects will be withdrawn from the study and he will be referred for treatment if necessary. Serious adverse events will be reported to IRB in no more than 24 hours after occurrence or after the psychiatrist is informed. In addition, this study will be fully compliant with the NIMH reportable events policy.

8.3.6 SERIOUS ADVERSE EVENT REPORTING

The study investigator shall complete an Unanticipated Adverse Device Effect Form and submit to the study sponsor and to the reviewing Institutional Review Board (IRB) as soon as possible, but in no event later than 10 working days after the investigator first learns of the effect. The study sponsor is responsible for conducting an evaluation of an unanticipated adverse device effect and shall report the results of such evaluation to the Food and Drug Administration (FDA) and to all reviewing IRBs and participating investigators within 10 working days after the sponsor first receives notice of the effect. Thereafter, the sponsor shall submit such additional reports concerning the effect as FDA requests.

8.3.7 REPORTING EVENTS TO PARTICIPANTS

N/A

8.3.8 EVENTS OF SPECIAL INTEREST

N/A

8.3.9 REPORTING OF PREGNANCY

Pregnancy will be assessed with a pregnancy test prior to the two MRI measurements. In the case of pregnancy, participation in the study is terminated, because of potential risks of MRI measurements for pregnant women.

8.4 UNANTICIPATED PROBLEMS

8.4.1 DEFINITION OF UNANTICIPATED PROBLEMS (UP)

The Office for Human Research Protections (OHRP) considers unanticipated problems involving risks to participants or others to include, in general, any incident, experience, or outcome that meets all of the following criteria:

- Unexpected in terms of nature, severity, or frequency given (a) the research procedures that are described in the protocol-related documents, such as the Institutional Review Board (IRB)-approved research protocol and informed consent document; and (b) the characteristics of the participant population being studied;
- Related or possibly related to participation in the research (“possibly related” means there is a reasonable possibility that the incident, experience, or outcome may have been caused by the procedures involved in the research); and
- Suggests that the research places participants or others at a greater risk of harm (including physical, psychological, economic, or social harm) than was previously known or recognized.

This definition could include an unanticipated adverse device effect, any serious adverse effect on health or safety or any life-threatening problem or death caused by, or associated with, a device, if that effect, problem, or death was not previously identified in nature, severity, or degree of incidence in the investigational plan or application (including a supplementary plan or application), or any other unanticipated serious problem associated with a device that relates to the rights, safety, or welfare of subjects (21 CFR 812.3(s)).

8.4.2 UNANTICIPATED PROBLEM REPORTING

The investigator will report unanticipated problems (UPs) to the reviewing Institutional Review Board (IRB) and to the Data Coordinating Center (DCC)/lead principal investigator (PI). The UP report will include the following information:

- Protocol identifying information: protocol title and number, PI's name, and the IRB project number;
- A detailed description of the event, incident, experience, or outcome;
- An explanation of the basis for determining that the event, incident, experience, or outcome represents an UP;
- A description of any changes to the protocol or other corrective actions that have been taken or are proposed in response to the UP.

To satisfy the requirement for prompt reporting, UPs will be reported using the following timeline:

- UPs that are serious adverse events (SAEs) will be reported to the IRB and to the DCC/study sponsor within 5 days of the investigator becoming aware of the event.
- Any other UP will be reported to the IRB and to the DCC/study sponsor within <insert timeline in accordance with policy> of the investigator becoming aware of the problem.
- All UPs should be reported to appropriate institutional officials (as required by an institution's written reporting procedures), the supporting agency head (or designee), and the Office for Human Research Protections (OHRP) within <insert timeline in accordance with policy> of the IRB's receipt of the report of the problem from the investigator.]

An investigator shall submit to the sponsor and to the reviewing Institutional Review Board (IRB) a report of any unanticipated adverse device effect occurring during an investigation as soon as possible, but in no event later than 10 working days after the investigator first learns of the effect (21 CFR 812.150(a)(1)). A sponsor who conducts an evaluation of an unanticipated adverse device effect under 812.46(b) shall report the results of such evaluation to the Food and Drug Administration (FDA) and to all reviewing IRB's and participating investigators within 10 working days after the sponsor first receives notice of the effect. Thereafter the sponsor shall submit such additional reports concerning the effect as FDA requests (21 CFR 812.150(b)(1)).

8.4.3 REPORTING UNANTICIPATED PROBLEMS TO PARTICIPANTS

N/A

9 STATISTICAL CONSIDERATIONS

9.1 STATISTICAL HYPOTHESES

Primary Efficacy Endpoint(s):

H0: Real rTMS has no superior effect over sham rTMS in reducing severity of AVH in schizophrenia (HCS score).
H1: Real rTMS has a superior effect over sham rTMS in reducing severity of AVH in schizophrenia (HCS score).

Secondary Efficacy Endpoint(s):

1. H0: Real rTMS has no superior effect over sham rTMS in reducing quality of AVH in schizophrenia (BAVQ-R score).
H1: Real rTMS has a superior effect over sham rTMS in reducing quality of AVH in schizophrenia (BAVQ-R score).
2. H0: Real rTMS has no superior effect over sham rTMS in reducing positive symptoms including AVH in schizophrenia (BPRS-subscale).
H1: Real rTMS has a superior effect over sham rTMS in reducing positive symptoms including AVH in schizophrenia (BPRS subscale).
3. H0: Real rTMS has no superior effect over sham rTMS in reducing severity of general psychopathology in schizophrenia (CGI score).
H1: Real rTMS has a superior effect over sham rTMS in reducing severity of general psychopathology in schizophrenia (CGI score).
4. H0: Real rTMS has no superior effect over sham rTMS in reducing global functioning in schizophrenia (GAF score).
H1: Real rTMS has a superior effect over sham rTMS in reducing global functioning in schizophrenia (GAF score).
5. H0: Real rTMS compared to sham rTMS does not impact cognitive functioning (RBANS).

H1: Real rTMS compared to sham rTMS does not impact cognitive functioning (RBANS).

6. H0: Response to rTMS is not predicted by neurophysiological characteristics.

H1: There are specific neurophysiological markers that predict response to rTMS.

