1 PROTOCOL SUMMARY

1.1 SYNOPSIS

Title: Boost rTMS for AVH – Therapeutic Response and Neurobiological Prediction Markers in Auditory Verbal Hallucinations

Study Description: This is a randomized, placebo controlled, double-blind clinical trial. We aim to examine the efficacy of repeated transcranial magnetic stimulation (rTMS) for the treatment of auditory verbal hallucinations (AVH) in patients with schizophrenia who are not taking antipsychotic medication. We employ a novel, accelerated protocol with only 4 sessions of low-frequency rTMS in one day. The effects of this accelerated protocol will be compared to the sham stimulation. Additionally, we will examine the effects of rTMS on a neurophysiological level by evaluation mechanism of action in the temporo-parietal lobe.

Objectives: Primary Objective:
Examine the efficacy of low-frequency rTMS for AVH in patients with a schizophrenia spectrum disorder.

Secondary Objectives:
Examine the effects of rTMS on the quality of AVH, positive symptoms, general psychopathology, and the global level of functioning of these patients. Last, confirm that rTMS has no side effects on cognitive functioning.

Determine the neuroimaging-related biomarkers associated with response to rTMS using the baseline imaging parameters (rCBF, resting fMRI, T1, and DTI) to predict response to rTMS treatment. Further,

compare pre- and post-treatment imaging parameters (rCBF, resting fMRI, T1, and DTI) to characterize rTMS effects on AVH.

Endpoints:

Primary Endpoint:

- AVH assessed using the Hallucination Change Scale (HCS) at baseline (first visit), after the last TMS session, after the post-MRI.

Secondary Endpoints:

- a) Assessment of the qualitative content of hallucinations will be assessed using the revised Beliefs About Voices Questionnaire (BAVQ-R)
- b) Assessment of AVH as part of positive symptoms will be assessed with the Brief Psychiatric Rating Scale (BPRS)-subscale that includes "Hallucinatory Behavior", "Conceptual Disorganization", "Suspiciousness", and "Unusual Thought Content".
- c) Global functioning will be assessed using the Clinical Global Impression (CGI) and General Assessment of Functioning (GAF) questionnaires.
- d) Cognitive functioning will be assessed using the Repeatable Battery for the Assessment of Neuropsychological Status (rBANS).

Neurophysiological changes using magnetic resonance imaging (MRI) are investigated as predictors for rTMS treatment response.

Study Population:

N = 40

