Examine the effects of rTMS on the global functioning of the patient with a schizophrenia spectrum disorder.	c) global function is assessed using the Clinical Global Impression (CGI) and the General Assessment of Functioning (GAF)	The global scores (CGI (Haro et al., 2003) and GAF (Jones, Thornicroft, Coffey, & Dunn, 1995)) nicely complement the specific measure and provide a complete picture of the patient's mental state.
Confirm that rTMS has no cognitive side effects.	d) The neuropsychological test Repeatable Battery for the Assessment of Neuropsychological Status (rBANS)	In order to confirm that rTMS has no undesirable cognitive side effects the rBANS is used as a standard cognitive measure.

Neurophysiological changes using magnetic resonance imaging (MRI) are investigated as predictors for rTMS treatment response.

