9.4 STATISTICAL ANALYSES

9.4.1 GENERAL APPROACH

Descriptive statistics will include all patients who completed the study. Patient groups (stratified according to either their sham or real rTMS treatment) will be compared concerning age, sex, socio economic status, general psychopathology (CGI, GAF), severity of AVH (BPRS-subscale, BAVQ-R), and cognitive outcome (rBANS). In particular, mean (standard deviation) together with the range (min, max) will be assessed for the two groups.

Inferential statistics: the p-value will be set to 5% and therefore every value below this threshold is considered significant. Effect sizes will be calculated as well to evaluate if we are dealing with a clinically important effect. Covariates will be included in the analyses such as age and sex.

General assumptions of heterogeneity and normality will be assessed before any subsequent analysis. Based on this either parametric or non-parametric tests will be chosen.

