9.4.3 ANALYSIS OF THE SECONDARY ENDPOINT(S)

Our secondary goal is to test if rTMS improves also the quality of AVH (BAVQ-R), positive symptoms (BPRS-subscale), general psychopathology (CGI), and global functioning (GAF). Further, we want to confirm that rTMS has no impact on cognitive functions (rBANS).

Therefore, we will compute a number of repeated ANCOVAs with time of measurements as the within-subject factor, group (treatment vs. placebo) as between subject's factor, and baseline BAVQ-R scores, the positive symptom BPRS-scale, the CGI, and GAF scores as covariates, respectively. Patients who drop out of the study will not be included in the analyses. Further, we will compare the rBANS scores of baseline with the outcome scores within patients.

Additionally, we want to test if baseline neuroimaging biomarkers can predict response to rTMS. Therefore, voxel-wise multiple regression analyses in our neuroimaging measures will be performed to reveal areas and networks which correlate with the baseline scores of the HCS. We will calculate structural and functional connectivity analyses.

Preprocessing, and overview of the neuroimaging measures:

Baseline metabolic neuronal activity

The treatment effect will be monitored by assessing the baseline resting metabolic neuronal activity measured by ASL (Philipp Homan et al., 2011; Kindler et al., 2012; Orosz et al., 2012). Additionally, variations in resting CBF may be used as covariates of nuisance in all the analysis steps described so far.

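### The rBANS hypothesis has identical H0 and H1 and compares real with sham, but its only planned test is within patients and cannot confirm cognitive safety

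*Combined protocol and SAP*

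**What the plan says.** **Hypotheses (section 9.1, secondary 5).** The null is "H0: Real rTMS compared to sham rTMS does not impact cognitive functioning (RBANS" and the alternative is "H1: Real rTMS compared to sham rTMS does not impact cognitive functioning (RBANS". Apart from the label they are the same sentence. Both compare real with sham.

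**Aim.** The synopsis (1.1) wants to "confirm that rTMS has no side effects on cognitive functioning". The table in section 3 says "In order to confirm that rTMS has no undesirable cognitive side effects the rBANS is used as a standard cognitive measure". Section 9.4.3 says "we want to confirm that rTMS has no impact on cognitive functions (rBANS".

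**Analysis (section 9.4.3).** The repeated-measures ANCOVAs with a group factor take "baseline BAVQ-R scores, the positive symptom BPRS-scale, the CGI, and GAF scores as covariates, respectively". rBANS is not in that list. It gets its own sentence: "we will compare the rBANS scores of baseline with the outcome scores within patients". No test is named, there is no group term, and the plan does not say whether arms are analysed separately or together.

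**Other mentions.** Section 9.4.1 lists rBANS among the variables on which the arms are compared, under descriptive statistics: "mean (standard deviation) together with the range (min, max) will be assessed for the two groups". It also plans effect sizes in general. No confidence interval, margin or sample size is given for rBANS. Section 9.4.4 adds only summary statistics for safety endpoints.

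**The concern.** There are three separate faults.

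1. With H0 and H1 identical, no result can favour one over the other.
2. The hypothesis is a between-arm contrast and the planned test is a within-patient one. The same instruments are repeated within a stay of 3 to 4 days (1.1 and 1.2), so the change in a treated patient mixes any rTMS effect with any gain from repeating the battery and any effect of time in hospital. The randomised sham arm is there to remove those components, and the planned test does not use it.
3. A non-significant result does not show absence of an effect, and there is no margin against which absence could be shown.

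A real cognitive decline could go unseen through low power, dilution if the arms are pooled, or an offsetting retest gain. The wording of the aim would then allow the null result to be reported as confirmed absence of cognitive side effects for a new accelerated schedule.

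**Working it through.** **What the sample size was built for.** Section 9.2 gives d = 0.9, 80% power, 5% alpha and 20 per arm. Normal approximation: 2 × (1.960 + 0.842)² / 0.9² = 19.4, so 20 per arm. The two-sided t-test gives 20.39, and power at 20 per arm is 79.2%. The figure of 40 therefore reproduces, apart from rounding, but it is sized for AVH and not for rBANS.

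**Inputs for rBANS.** From the plan: 20 per arm and alpha 5%, taken as two-sided. Assumed, because the documents give no values: all 40 patients complete; changes are normal with SD 1; the true decline d occurs in the real arm only; the retest gain g is equal in both arms.

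**1. Within-patient test, no retest gain (noncentral t).**
- Real arm only, n = 20, noncentrality d√20. For d = 0.5, power is 56.5%, so 44% are missed. For d = 0.3, power is 24.7%, so 75% are missed.
- Arms pooled, n = 40. The mean change is d/2 and the SD is √(1 + (d/2)²). For d = 0.5, the mean is 0.25 and power is 32.2% (33.8% if the SD is left at 1), so 66 to 68% are missed. For d = 0.3, power is 15.0%, so 85% are missed.

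**2. Adding a retest gain, d = 0.5 (simulation, 200,000 runs).** Percentage of trials that detect the decline:

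| Assumed gain (SD of change) | Paired, real arm | Paired, pooled | Between-arm t-test on change |
|---|---|---|---|
| 0 | 56.3% | 31.6% | 33.8% |
| 0.25 | 18.5% | 2.2% | 33.5% |
| 0.5 | 2.5% | 0.0% | 33.8% |

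At a gain of 0.5 the mean change in the real arm is 0.5 − 0.5 = 0, so the paired test finds nothing beyond its error rate. The pooled mean is then +0.25, and the pooled test shows a significant *improvement* in 31.6% of trials although rTMS does harm. The between-arm test does not move, because the gain cancels.

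**3. What the between-arm ANCOVA can deliver.** In baseline SD units, SE = √(2/20) × √(1 − r²), where r is the baseline-to-final correlation (assumed). Residual df = 40 − 3 = 37 and t = 2.026. At r = 0.5: SE = 0.316 × 0.866 = 0.274, and the half-width is 2.026 × 0.274 = 0.555.

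| r (assumed) | 95% CI half-width | Power to exclude harm of 0.5 baseline SD | Power to exclude ±0.5 baseline SD |
|---|---|---|---|
| 0.5 | 0.555 | 43% | 2% |
| 0.7 | 0.458 | 58% | 18% |
| 0.8 | 0.384 | 73% | 46% |
| 0.9 | 0.279 | 94% | 88% |

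Both power columns take a true difference of 0 and use the 95% CI. The third column concerns harm only; the fourth needs the whole interval inside the margin. The 0.5 margin is illustrative.

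**Units.** Steps 1 and 2 use SD of change and step 3 uses baseline SD. With equal variances, SD of change = √(2(1 − r)) baseline SD, so 0.5 SD of change equals 0.50, 0.39, 0.32 or 0.22 baseline SD at the four values of r. For a decline of that size the ANCOVA has power of 43%, 39%, 37% or 35%, against 34% for the t-test on change.

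**The case against.** The duplicated sentence is very likely a stray negative in H1, since the other five secondary pairs oppose each other. One word repairs it. That is fair, but the repair leaves the mismatch of test and hypothesis, and the wording of the aim, untouched.

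Some between-arm intent is visible. The hypothesis names real and sham, section 9.4.1 summarises rBANS by arm and plans effect sizes, and the ANCOVA sentence follows directly on the rBANS goal. A gross imbalance would show in the tables. None of this specifies a real-versus-sham test, and the ANCOVA list omits rBANS.

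Nothing says the arms are pooled, so the pooled figures describe one possible reading. The decline, the retest gain and the SD are assumptions, so the figures illustrate the problem and do not measure it. With no retest gain, the paired test in the real arm is more powerful than the between-arm test (56% against 34%). The argument for changing it is validity, not sensitivity. These points stand.

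Section 9.2 calls the trial an exploratory pilot, in which an rBANS margin or power calculation would not be expected, and section 8.3.5 monitors side effects by the study physician, self-report and a side-effect scale. This lowers the consequence. It does not support an aim to confirm, since a pilot of 40 has less basis for that than a larger trial.

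**Conclusion.** The concern holds and should be fixed. The identical hypotheses, the within-patient test set against a real-versus-sham hypothesis, and the aim to confirm absence without a margin can all be read directly from the text and rest on no assumption.

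The size depends on values the documents do not give. For a decline of 0.5 SD of change confined to the real arm, with 20 completers per arm, the paired test in that arm misses it 44% of the time with no retest gain, 81% with a gain of 0.25 SD and about 97% with a gain of 0.5 SD. If the arms are pooled, it is missed 66 to 68%, 98% and practically always. The between-arm test removes the bias but is itself weak at this sample size, so an estimate with its confidence interval is the realistic output. The primary HCS analysis is not affected.

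**What to change.** 1. **Section 9.1, secondary 5.** H0: baseline-adjusted final rBANS does not differ between real and sham. H1: it differs.
2. **Section 9.4.3.** Analyse final rBANS by ANCOVA with group and baseline rBANS, and report the real-minus-sham difference with its 95% CI. State whether age and sex, which section 9.4.1 mentions as covariates, are included; adding both would take the residual df from 37 to 35. Keep the within-patient change as a description by arm.
3. **Sections 1.1, 3 and 9.4.3.** Replace the aim to confirm that rTMS has no cognitive side effects with the aim to estimate its effect on cognition. Claim absence of harm only if the investigators set and justify a margin in advance and the interval excludes it. State whether the margin is for harm only or for a difference in either direction.

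**Cost.** No new data, visits or patients: rBANS is already collected at baseline and at the final visit in both arms. One secondary analysis and the wording of one objective change. The downside is that the interval will be wide, about 0.28 to 0.55 baseline SD on each side over the assumed correlations, so the trial may be unable to claim cognitive safety.
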